#### **10.14** Response Criteria for the Patients with ALL

**Complete Remission (CR):** All of the following must be achieved:

- BM blasts <5% (M1 BM and adequate marrow cellularity);
- Absence of circulating blasts or extramedullary disease;
- Absolute neutrophil count (ANC)  $\ge 0.75 \times 10^9 / L$
- Platelet count  $\geq 75 \times 10^9/L$

Qualifying marrow and peripheral counts should be performed within 1 week of each other.

Morphological CR with partial recovery of platelet count (CRp): All of the following must be achieved:

- BM blasts <5% (M1 BM);
- Absence of circulating blasts or extramedullary disease;
- Recovery of ANC ≥750/mcL
- Insufficient recovery of platelets (< 75 000/mcl).

Morphological CR with incomplete count recovery (CRi): All of the following must be achieved:

- BM blasts <5% (M1 BM);
- Absence of circulating blasts or extramedullary disease;
- No recovery of ANCs (ANC < 750/mcl)
- Insufficient recovery of platelets (< 75 000/mcl).

**Partial Remission (PR):** All of the following must be achieved:

- Complete disappearance of circulating blasts and achievement of M2 BM status (5-25% blasts), without new sites of extramedullary disease;
- Recovery of ANCs (ANC > 750 mcL).

**Partial Remission** – **Cytolytic (PRCL):** Complete disappearance of circulating blasts and achievement of at least 50% reduction from baseline in BM blast count.

**Stable Disease (SD):** The patient does not satisfy the criteria for PD, or has recovery of ANC > 750 mcL and fails to qualify for CR, CRp, or PR.

**Progressive Disease (PD):** An increase of at least 25% in the absolute number of circulating leukemic cells, measured pre-therapy or during the first 14 days following start of therapy; or other laboratory or clinical evidence of PD, with or without recovery of ANC or platelets.

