## 9. Organ Function Requirements:

- a. Adequate BM Function Defined as
  - i. Peripheral absolute neutrophil count (ANC)  $\geq$ 0.75 x 10^9/L or 750/mm^3.
  - ii. Platelet count ≥75 x 10^9/L or 75,000/mm^3 (transfusion independent, defined as not receiving platelet transfusions for at least 7 days prior to enrollment.

- iii. Hemoglobin  $\geq 90g/L$  (transfusion permitted).
- iv. Patients with known BM metastatic disease or haematological malignancies will be eligible for study provided they meet haematological criteria. These patients may receive transfusions (e.g. to achieve platelet threshold) provided they are not known to be refractory to platelet transfusions but will not be evaluable for hematologic toxicity.

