If iUPD is not confirmed at the next assessment, then the appropriate response will be assigned (iUPD if the criteria are still met, but no worsening, or iSD, iPR or iCR if those criteria are met compared to baseline). The prior documentation of iUPD does not preclude assigning iCR, iPR, or iSD in subsequent time-point assessments or as best overall response (BOR) providing that iCPD is not documented at the next assessment after iUPD. Tumour disease evaluation will be by objective response rate (ORR = complete response [CR] and partial response [PR]). Patients with response of 'stable disease' (SD), iCR, iPR, or iSD will also be reported as part of the final analysis of clinical benefit, but will not contribute to the primary efficacy outcome measure (Seymour, 2017).

Treatment beyond initial iUPD is permitted in patients who are clinically stable to continue on treatment until the next assessment (≥four [4] weeks later); this next imaging assessment should

be no longer than eight (8) weeks later, to ensure that patients remain fit for salvage therapies All decisions regarding continuation or discontinuation of therapy should be made by the patient, the local PI and either the Study Chair or Co-Chair. An assignment of clinical stability requires that no worsening of performance status has occurred, that no clinically relevant increases in disease-related symptoms such as pain or dyspnoea occur that are thought to be associated with disease progression, and that no requirement for intensified management of disease-related symptoms exists, including increased analgesia, radiotherapy, or other palliative care.

Patients who have iUPD and are not clinically stable should be designated as not clinically stable in the case report form. This designation will allow the best overall response to be calculated and the date of iUPD to be used in estimates of PFS.

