## 10.13 Response Criteria for Patients with AML

The AML response criteria are derived according to Creutzig, *et al.* (2004, 2012) with some revisions from the AML International Working Group (IWG) Criteria (Cheson, 2003).

The following definitions will be used:

**Complete remission (CR):** All of the following must be achieved:

- BM blasts <5% (M1 BM);
- Absence of circulating blasts or extramedullary disease;
- Absolute neutrophil count (ANC)  $\geq 1.0 \times 10^9 / L$ ;
- Platelet count  $\geq 80 \times 10^9/L$ .

Occasionally, a rare peripheral blood blast may be identified during marrow regeneration; however, the marrow must be M1 status and with no Auer rods. Flow cytometry may also be useful to distinguish between leukemia and a regenerating BM. There is no requirement for BM cellularity.

Morphological CR with partial recovery of platelet count (CRp): All of the following must be achieved:

- BM blasts <5% (M1 BM) with no Auer rods;
- Absence of circulating blasts or extramedullary disease;
- Recovery of ANC  $\geq 1.0 \times 10^9 / L$ ;
- Platelet transfusion independence (defined as, no platelet transfusions for 1 week).

Morphological CR with incomplete count recovery (CRi): All of the following must be achieved:

- BM blasts <5% (M1 BM) with no Auer rods;
- Absence of circulating blasts or extramedullary disease;
- All CR criteria except for residual neutropenia (<1.0 x 10^9/L) or thrombocytopenia (<80 x 10^9/L) without platelet transfusion independence (defined as, no platelet transfusions for 1 week).

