#### Cytogenetic complete remission (CRc):

- The patient must also have attained and be assigned morphologic response of CR or CRp or CRi as defined above.
- Must have a revision to a normal karyotype with a minimum analysis of 20 metaphases.

**Partial Response (PR):** A decrease of at least 50% blasts percentage (to M2: 5% to 25%) in the BM aspirate. BM must have adequate cellularity (e.g., > 15%) to determine response. PR status will not be included in calculation of response to the regimen.

A repeat BM aspiration after several weeks may be required to distinguish between a PR and increased blasts caused by BM regeneration. A value of < 5% blasts may also be considered a PR if Auer rods are present.

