#### **Treatment Failure (TF):**

- Failure to achieve CR or CRi
  - Any M2 (5-25% blasts) or M3 (5-25% blasts) BM aspirate that does not qualify for PR status;
  - M1 (5% blasts) BM aspirate with evidence of circulating blasts or extramedullary disease;

**Relapse:** Morphologic relapse after CR/CRp/CRi is achieved and documented, defined as:

- A reappearance of leukemic blasts in the peripheral blood or ≥ 5% blasts (M1) in BM not attributable to any other cause (such as, BM regeneration after consolidation therapy).
- If there are no circulating blasts, but the BM contains 5% to 25% blasts (M2)
  - A repeat BM performed at least a week later is necessary to distinguish relapse from BM regeneration.
- The reappearance or development of cytologically proven extramedullary disease;
  - Molecular and/or genetic relapse is characterized by reappearance of a cytogenetics or molecular abnormality.

Should flow cytometry analyses suggest relapse (by the reappearance of a similar immunophenotype to the original leukemia) in the presence of < 5% blasts, or  $\ge 5\%$  blasts in a regenerating marrow, a repeat BM aspirate performed at least a week later is necessary to confirm relapse by morphologic methods. In such instances, the date of recurrence is defined as the first date that  $\ge 5\%$  blasts were observed (in BM).

**Unevaluable:** Aplastic or severely hypo-cellular marrow with any blast percentage. In this instance, marrow evaluation should be repeated weekly until response determination can be made through at least Day 49.

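### Leukaemia rules do not fit the CR+PR count: ALL marrow clearance with neutrophil-only non-recovery is neither CR, CRp, CRi nor PR, and AML PR is excluded in 10.13 but counted in Section 11

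*Protocol*

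**What the plan says.** Section 10.2.7 defines the endpoint: "Tumour disease evaluation will be by objective response rate (ORR = complete response [CR] and partial response [PR". The synopsis gives the same definition, refers to Section 10.13 for AML and Section 10.14 for ALL, and says that stable disease does not contribute to the primary measure. Section 11 closes a cohort at 1 or fewer responses in 10. It declares activity at 5 or more of 20 (Cohort A) or 6 or more of 30 (Cohort B), each time counting CR+PR.

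Leukaemia patients can enter. Section 4.2.2, item 9a, states: "Patients with known BM metastatic disease or haematological malignancies will be eligible for study provided they meet haematological criteria".

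For ALL, Section 10.14 lists the CRi conditions as all required. They include "No recovery of ANCs (ANC < 750/mcl" and "Insufficient recovery of platelets (< 75 000/mcl". For AML, Section 10.13 words CRi as "All CR criteria except for residual neutropenia" or thrombocytopenia, so either one is enough.

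On AML partial response, Section 10.13 says: "PR status will not be included in calculation of response to the regimen". Its treatment-failure entry opens with "Failure to achieve CR or CRi" and does not name CRp.

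**The concern.** Sections 10.13 and 10.14 decide whether a leukaemia patient is a responder in the Section 11 count.

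- **ALL.** The conjunction in CRi leaves a gap. A cleared marrow with neutrophil-only non-recovery has no complete-remission label, while a marrow still holding 5-25% blasts can be PR.
- **AML.** A PR is a responder under the words of Section 11 and a non-responder under the words of Section 10.13.
- **Minor.** The AML failure line omits CRp, although the relapse and cytogenetic-remission entries group CR, CRp and CRi together.

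With bars of 2, 5 and 6 responses, one patient's label can decide a cohort.

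**Working it through.** **1. ALL categories.** Inputs are the Section 10.14 definitions. Take a post-treatment marrow of 4% blasts with no circulating or extramedullary disease.

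| ANC (/mcL) | Platelets (/mcL) | CR | CRp | CRi | PR |
|---|---|---|---|---|---|
| 1000 | 100 000 | yes | no | no | no |
| 1000 | 50 000 | no | yes | no | no |
| 500 | 50 000 | no | no | yes | no |
| 500 | 100 000 | no | no | no | no |

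The last row fails CR on ANC, CRp on both counts, CRi on platelets, and PR on both marrow grade (5-25% needed) and ANC (above 750 needed).

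Two labels remain for that row.

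- *PRCL* needs cleared circulating blasts and a fall of at least 50% in marrow blasts. It has no count condition. From a baseline of 6%, half is 3%, and 4% does not reach it. From 8%, half is 4%, which just qualifies. From 10% or more, any marrow under 5% qualifies automatically.
- *SD* has two alternatives joined by an or. The first is only that the patient does not meet PD, so this patient meets it. Read literally, so does a patient in CR.

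The row is therefore SD alone from a 6% baseline, and PRCL and SD together from 8%, 10% or 40%. By contrast, 20% blasts with cleared blood, no new extramedullary site and ANC above 750 is PR and counts.

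**2. AML PR, side by side.** The synopsis, Section 10.2.7 and Section 11 all count PR. Section 10.13 leaves AML PR out, and Section 11 does not carry that exception.

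**3. AML failure line.** Two situations are listed beneath it: an M2 or M3 marrow not reaching PR, and an M1 marrow with circulating blasts or extramedullary disease. A CRp patient has an M1 marrow with neither, so fits neither situation.

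**4. What one patient changes.** The plan's own figures come first.

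- *Power:* sum over x = 2 to 10 of P(Bin(10, p) = x) × P(Bin(n₂, p) ≥ r − x). Cohort A (n₂ = 10, r = 5, p = 0.35) gives 0.843, stated 85%. Cohort B (n₂ = 20, r = 6, p = 0.30) gives 0.815, stated 80%. The bars work as described.
- *Posterior:* Beta(1 + x, 1 + n − x), assuming a uniform prior. For 5/20, P(RR > 0.2) = 0.77; for 6/30 it is 0.57. Both match the protocol.

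Now take away one response:

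| Counted | One fewer | Rule outcome | P(RR > 0.2) |
|---|---|---|---|
| 2/10 | 1/10 | cohort closes | not applicable |
| 5/20 | 4/20 | null not rejected | 0.77 to 0.59 |
| 6/30 | 5/30 | null not rejected | 0.57 to 0.39 |

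**The case against.** **A specific rule governs a general one.** The synopsis takes CR and PR as defined by the disease criteria, including Section 10.13, so the AML exclusion can be read as part of the definition. That gives a workable reading. It does not remove the conflict, because Section 11 states the decision rule as CR+PR with no exception.

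**A responder mapping may sit in an analysis plan that is not shown.** This is fair, and its absence is not the point. The ALL conjunction and the AML exclusion are both stated in the protocol, and an analysis plan could settle the AML conflict only by setting one statement aside.

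Four stronger readings are tempting, and the documents do not support them.

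- *The ALL patient simply falls to stable disease.* PRCL also applies once marrow blasts have halved, and its name contains partial remission. If PRCL counts, that patient is not ranked below a PR.
- *CRp and CRi have no home.* Both are titled as morphological CRs, and Section 10.13 groups them with CR in the cytogenetic-remission and relapse entries. The natural reading is that they count as CR.
- *An AML CRp patient is a treatment failure.* The two listed failure situations do not fit such a patient. This is an omitted abbreviation.
- *About a third of patients are exposed.* That figure in Section 1.1 covers leukaemia and lymphoma together, in CMMRD patients. Lymphoma is scored under Section 10.15, and enrolment now extends beyond CMMRD.

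The ANC-only case also needs a fall on treatment, since entry requires ANC of at least 750/mm³.

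**Conclusion.** Two rules are wrong as written: the both-required condition in ALL CRi, and the AML PR exclusion that Section 11 does not carry. The CRp omission is minor. Following the text can misclassify a leukaemia patient for the primary endpoint.

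The size is one response for each affected patient, against bars where one response can close a cohort or reverse its conclusion. Practical weight is low. The protocol does not give the number of leukaemia patients, it is probably small, and only those in Cohorts A or B enter the two bars. A reader might quote the chance that a cohort ends one response short as the size of the problem. That chance does not measure it: a leukaemia patient in an affected category and a cohort at its bar would both be needed, and the documents give no basis for the joint probability.

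**What to change.** **Section 10.14.** Define ALL CRi as under 5% marrow blasts, no circulating or extramedullary disease, and ANC below 750/mcL whatever the platelet count. CRp keeps platelet-only non-recovery. Every cleared ALL marrow then has exactly one label among CR, CRp and CRi. Limit ALL SD to patients who meet no response category and do not meet PD.

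**Section 11.** State one leukaemia responder rule:

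- CR, CRp and CRi count as CR.
- AML PR is reconciled with Section 10.13, either by carrying the exclusion into Section 11 or by deleting that sentence.
- ALL PR and PRCL are each stated as counting or not counting.

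**Section 10.13.** Add CRp to the AML failure line.

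The cost is amendment wording. The blood counts and marrow evaluations needed are already in the Section 8.2 calendar. The change should be made before leukaemia responses are classified.

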# Exclusion Criteria (Part II only):

to first dose of trial therapy or while on trial are not eligible. The use of physiologic doses of corticosteroids (up to 5mg/m²/day prednisone equivalent) is permitted following discussion with the Study Chair or Co-Chair.

Note: Use of topical, ocular, intra-articular, intra-nasal or inhaled corticosteroids will not render a patient ineligible. A brief course of corticosteroids for prophylaxis (e.g. contrast dye allergy) or for treatment of non-autoimmune conditions (e.g. delayed-type hypersensitivity reaction caused by contact allergen) is permitted if completed at least 7 days prior to initiation of therapy.

- b. **Investigational Drugs:** Patients who are currently receiving another investigational drug are not eligible.
- c. Anti-cancer Agents: Patients who are currently receiving other anticancer agents are not eligible.
- 3. Patients with a History of Autoimmune Disease
- Patients with a history of autoimmune disorder that has required systemic treatment in the previous two (2) years are not eligible.
   Asymptomatic laboratory abnormalities (e.g. ANA, rheumatoid factor, altered thyroid function studies) will not render a patient ineligible in the absence of a diagnosis of an autoimmune disorder. Replacement therapy (e.g. thyroxine, insulin or physiologic corticosteroid replacement therapy) is not considered a form of systemic treatment.
- **4. Infection:** Patients who have an uncontrolled infection are not eligible.
- **5. HIV and/or Hepatitis B/C patients:** Patients with known HIV/AIDS or acute/chronic Hepatitis B or C are excluded.
- **6. Transplant patients:** Patients who have received prior allogeneic Bone Marrow (BM) transplants or prior solid organ transplantation are not eligible.
- **7. Non-Compliance:** Patients who in the opinion of the investigator may not be able to comply with the safety monitoring requirements of the study are not eligible.

	8. Previous anti-PD-1 and/or anti-PD-L1 therapy: Patients who have				
	received prior anti-PD-1 and/or anti-PD-L1 directed therapy (mAb or				
	small molecule) are not eligible.				
	9. Live vaccines: Patients who have received a live vaccine within 30				
	days of start of study treatment are not eligible.				
	Primary efficacy outcome measures:				
	Tumour disease evaluation, includes objective response rate (ORR =				
	complete response [CR] and partial response [PR]) as defined by iRECIST				

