	response criteria for solid tumours (revised for neuroblastoma using the				
	revised INRC), iRANO response criteria for CNS malignancies, RECIL				
	2017 response criteria for lymphomas, revised criteria according to				
	Creutzig, et al. (2012) for acute myeloid leukemia (AML; see Section				
	10.13), and response criteria as specified in Section 10.14 for acute				
Criteria for	lymphoblastic leukemia (ALL).				
Efficacy	Patients with response of 'stable disease' (SD) will also be reported as part				
Evaluation:	of the final analysis of clinical benefit, but will not contribute to the				
	primary efficacy outcome measure.				
	Secondary efficacy outcome measures:				
	PFS is defined as the time from the first dose of the study drug				
	administration to the occurrence of disease progression or death from any cause during the study.				
	OS is defined as time from first dose of study drug to death from any				
	cause.				
	A safety evaluation by the Safety Committee will be performed after				
Criteria for	Patient 1-Cycle 1, Patient 4-Cycle 1, Patient 7-Cycle 1, and Patient 10-				
Safety	Cycle 1. Enrollment will be held after each time point until a safety				
Evaluation:	evaluation of adverse events (AE) and serious adverse events (SAE)				
	confirms it is safe to resume enrollment.				
	confirms it is safe to resume enrollment.				

Toxicities will be described and defined in paediatric patients, focusing on SAEs, using the National Cancer Institute Common Terminology Criteria for Adverse Events (NCI CTCAE), version 4.03. Toxicities (drug-related AEs) of any grade, plus all Grade  $\geq$  3 AEs, all Grade  $\geq$  3 laboratory toxicities and all SAEs as defined in *Section 12* will be collected for this study.

The initial aim for this pilot study was to accrue 20 paediatric patients with biallelic mismatch repair disease (bMMRD) tumours. Following amendment, the study inclusion criteria are expanded to include those with hypermutant tumours (as determined by estimation of TMB by targeted next-generation gene sequencing), as well as patients with CMMRD tumours. Consequently, the total enrollment will be increased to 50 patients.

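### ALL partial remission needs no fall in marrow blasts from baseline, so an unchanged patient can count as a responder in the primary ORR

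*Protocol*

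**What the plan says.** The synopsis names the primary efficacy measure: "Tumour disease evaluation, includes objective response rate (ORR" is set equal to complete plus partial response. For ALL it applies "response criteria as specified in Section 10.14 for acute" lymphoblastic leukaemia, so an ALL PR under Section 10.14 enters the primary endpoint.

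Section 10.14 lists the PR elements, all of which must be met:
- for blood, marrow and extramedullary sites, "Complete disappearance of circulating blasts and achievement of M2 BM status (5-25% blasts), without new sites of extramedullary disease";
- for neutrophils, a count that has recovered to above 750/mcL.

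The next category in that section, cytolytic partial remission (PRCL), does refer to baseline: it needs clearance of circulating blasts and "achievement of at least 50% reduction from baseline in BM blast count". SD covers a patient who does not meet the criteria for progression or, alternatively, one whose ANC has recovered without reaching CR, CRp or PR.

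In AML (Section 10.13), PR begins with "A decrease of at least 50% blasts percentage", and the same paragraph leaves PR out of the calculation of response.

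Leukaemia is admitted: "Patients with known BM metastatic disease or haematological malignancies will be eligible for study provided they meet haematological criteria" (Section 4.2.2, criterion 9a). Those criteria include an ANC of at least 0.75 x 10^9/L.

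**The concern.** A response category that feeds an objective response rate should record a change under treatment. ALL PR is written as a state to be found at re-evaluation. A patient already in that state at entry can be scored a responder although nothing has happened, and a marrow that drifts across the 25% boundary is scored the same way.

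The decision rules are small: close at 1 or fewer responses in 10; reject the null at 5 of 20 (Cohort A) or 6 of 30 (Cohort B). One response credited without a treatment effect can keep a cohort open, or supply the response that rejects the null. Because the same unchanged patient also fits SD, two sites could score the same marrow differently.

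**Working it through.** **1. The definition applied to an unchanged patient.** Take 15% marrow blasts, none circulating, no extramedullary disease and ANC above 750/mcL, the same at baseline and re-evaluation.

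| Category in Section 10.14 | What it asks | Result |
|---|---|---|
| PR, blood | no circulating blasts | met |
| PR, marrow | 5-25% blasts | met |
| PR, extramedullary | no new site | met |
| PR, ANC | above 750/mcL | met; entry already requires at least 750/mcL |
| PRCL | at least 50% fall from baseline | not met (0% fall) |
| SD, first clause | progression criteria not met | met |
| CR | marrow below 5% | not met |

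PR and SD are both satisfied and no order is given. A marrow going from 26% to 24% also meets the PR marrow element, with a relative fall of (26 - 24)/26 = 7.7%.

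**2. The plan's own design figures.** Inputs from Section 11: n1 = 10, close if X1 <= 1; Cohort A has n = 20 and rejects at r = 5; Cohort B has n = 30 and rejects at r = 6. The null is 10% for A; for B no null is restated, so 10% is assumed.

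P(reject) = sum over x >= 2 of P(X1 = x) * P(X2 >= r - x), with X1 ~ Bin(10, p) and X2 ~ Bin(n - 10, p).

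Cohort A at p = 0.10, for x = 2, 3, 4 and then x >= 5: 0.19371*0.07019 + 0.05740*0.26390 + 0.01116*0.65132 + 0.0016 = 0.0136 + 0.0151 + 0.0073 + 0.0016 = 0.0376.

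| | Power, stated | Power, exact | Type I error, stated | Type I error, exact |
|---|---|---|---|---|
| A (35%) | 85% | 0.843 | 0.05 | 0.0376 |
| B (30%) | 80% | 0.815 | 0.05 | 0.0525 |

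Power reproduces. The stated 0.05 is nominal; nothing here rests on the difference.

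**3. One patient scored PR with certainty, all others at 10%.** With that patient in stage 1, X1 = 1 + Bin(9, 0.10); in stage 2, X2 = 1 + Bin(n - 11, 0.10).

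| Position | A | B |
|---|---|---|
| Stage 1 | 0.1100 | 0.1417 |
| Stage 2 | 0.0916 | 0.1016 |

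If the patient is equally likely to be any of the n:
- A: (10/20)*0.1100 + (10/20)*0.0916 = 0.101
- B: (10/30)*0.1417 + (20/30)*0.1016 = 0.115

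Two such patients placed at random give 0.235 (A) and 0.225 (B) by the same weighting over positions.

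**4. Stage 1 closure at the null.** With none, P(X1 <= 1) = 0.736. With one such patient in stage 1, closure needs no response among the other nine: 0.9^9 = 0.387. With two, closure cannot occur.

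**The case against.** The best reply is that the PR wording is not purely a state. It speaks of disappearance, achievement and recovery, and read naturally a marrow at 20% throughout has not achieved anything. That has some force for intent. It does not settle scoring: no amount of change is given, the words have nothing to act on in a patient with no circulating blasts and an adequate ANC at entry, and SD overlaps without a tie-break.

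It is also fair that the 50% fall in AML PR is not the standard that ALL departs from, because AML PR never enters the response rate. The comparison that holds is within Section 10.14, between PR and PRCL.

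Three stronger readings are tempting, and the documents do not support them:
- *A reader might infer that ALL CR has the same flaw.* Part II requires recurrent or refractory disease that is measurable or evaluable (Section 4.2.2, criterion 5), and Section 11 ties evaluability to Section 10.2.1.2, which, apart from early progressors, looks for disease present at baseline. CR therefore normally implies a change, even though its count thresholds match the entry thresholds.
- *A reader might extend it to AML, or argue that "Molecular and/or genetic relapse is characterized by reappearance of a cytogenetics or molecular abnormality" admits patients already below 5% blasts.* AML PR is excluded from response. The molecular-relapse line gives no blast level and concerns loss of response in AML. The nearby flow-cytometry text asks for morphologic confirmation.
- *A reader might take the background statement that about one third of CMMRD patients develop leukaemia or lymphoma as the expected number.* It pools two diseases, counts lifetime occurrence rather than trial entrants, and says nothing about marrow burden.

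**Conclusion.** The point holds for ALL PR alone. As written, Section 10.14 allows a patient with an unchanged M2 marrow, no circulating blasts and the entry ANC to count in the primary ORR, and it gives no rule for choosing between PR and SD.

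One such patient would raise type I error from 0.038 to 0.101 in Cohort A and from 0.053 to 0.115 in Cohort B, roughly 2.7 and 2.2 times. These figures illustrate sensitivity; they do not predict what will happen. They rest on a 10% null in both cohorts, an assumed count of one, random placement between stages, and that patient being scored PR with certainty. The text shows only that such a score is possible. If no such patient enrols, the error rates are unaffected.

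**What to change.** For endpoint scoring in Section 10.14 only:
1. State that a PR whose criteria were already met at baseline does not count in ORR and is scored SD.
2. Require for PR a stated reduction in marrow blasts from baseline; the 50% already used for PRCL is available.
3. State the precedence between PR and SD, and whether PRCL counts in ORR. If the 50% is adopted, every PR also meets PRCL, so this has to be settled at the same time.

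A minimum marrow blast level for evaluability is not a suitable substitute: it could drop a patient with circulating blasts and a marrow below 5%, who has active disease. CR and the AML section need no change on this account.

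The cost is a few sentences, best settled before response data are read. No new assessment is needed, since Section 8.2 already schedules marrow evaluation for leukaemia. A few low-burden ALL patients would be scored SD rather than PR, so the ORR may be slightly lower.
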